PROTOCOL

Predictive value of suPAR and hsCRP on postoperative mortality in 951 patients undergoing elective on-pump cardiac surgery.

TABLE OF CONTENTS

| | |
|---|----|
| Project summary | 3 |
| General information | 4 |
| Rationale & background information | 5 |
| Study goals and objectives | 7 |
| Study design | 8 |
| Methodology | 9 |
| Safety considerations | 10 |
| Follow-up | 10 |
| Data management and Statistical Analysis | 10 |
| Quality Assurance | 11 |
| Expected Outcomes of the Study | 11 |
| Dissemination of Results and Publication Policy | 11 |
| Duration of the Project | 12 |
| Problems Anticipated | 12 |
| Project Management | 12 |
| Ethics | 13 |
| Informed Consent Forms | 14 |
| Financing and insurance | 18 |

PROJECT SUMMARY

Title: Predictive value of suPAR and hsCRP on postoperative mortality in 951 patients undergoing elective on-pump cardiac surgery.

The risk models currently used to predict outcome after cardiac surgery only explain a minor part of the observed variation in perioperative complications between patients. A recent trend in risk modelling has been the addition of various biomarkers to supplement clinical risk factors.

This study aims to investigate whether preoperative measurement of the inflammatory biomarkers soluble urokinase plasminogen activating receptor (suPAR) and High-sensitivity C-Reactive Protein (hsCRP) are associated with death after cardiac surgery. Further, to assess whether suPAR and hsCRP provides increased predictive accuracy of the clinical risk model EuroSCORE II. The purpose of the study is to gain knowledge on whether these inflammatory biomarkers might be able to reveal a pro-inflammatory disease state that represents a risk in patients undergoing cardiovascular surgery. Hence, these biomarkers may assist clinicians to gain more accurate risk identification and selecting compassionate treatment for high risk patients.

The study design is a retrospective observational cohort study conducted at The Department of Cardiothoracic Anaesthesiology, Rigshospitalet, in collaboration with University of Copenhagen and PERSIMUNE Centre of Excellence, Rigshospitalet.

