HsCRP has received a lot of attention regarding screening, reclassification and prediction of treatment response in patients suffering from cardiovascular disease, and elevated levels of hsCRP preoperatively was found to be associated with increased risk of postoperative cardiovascular events after on-pump coronary artery bypass grafting surgery (Yousuf et al. 2013, Balciunas et al. 2009). A Danish study from 2018 has revealed, that elevated suPAR and CRP were associated with cardiovascular risk and had predictive value among the 60-year old, and suPAR was of particular importance among women (Diedrichsen et al. 2018). Hence, these inflammatory biomarkers might be able to reveal a pro-inflammatory disease state that represents a risk in patients undergoing cardiovascular surgery, leading to a stronger inflammatory response with subsequent increased morbidity and mortality.

STUDY GOALS AND OBJECTIVES

The goals of this study are to assess how a high pro-inflammatory disease state at baseline reflected by the biomarkers suPAR and hsCRP, is associated with adverse outcome after cardiac surgery. We also expect that suPAR and/or hsCRP can provide increased predictive accuracy of the risk model EuroSCORE II which is currently being used for risk stratification in many hospitals.

Primary objective

1. Association of preoperative suPAR values in relation to the censored time-to-event outcome “death from any cause” [Time Frame: from index surgery to date of data collection]

Secondary objectives:

1. Association of preoperative hsCRP values in relation to the censored time-to-event outcome “death from any cause” [Time Frame: from index surgery to date of data collection]
2. Assess whether adding suPAR, hsCRP or combined suPAR+hsCRP measurements improves predictive accuracy of EuroSCORE II [Time Frame: from index surgery to 30 days postoperative]
3. Sensitivity of the models; EuroSCORE II, suPAR, hsCRP, suPAR+hsCRP, EuroSCOREII+suPAR, EuroSCOREII+hsCRP and EuroSCOREII+suPAR+hsCRP in relation to the time-to-event outcome “death from any cause” [Time Frame: from index surgery to 30 days postoperative]
4. Specificity of the models; EuroSCORE II, suPAR, hsCRP, suPAR+hsCRP, EuroSCOREII+suPAR, EuroSCOREII+hsCRP and EuroSCOREII+suPAR+hsCRP in relation to the time-to-event outcome “death from any cause” [Time Frame: from index surgery to 30 days postoperative]
5. Asses association between suPAR and hsCRP measurements

Other outcome measures:

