A table 2 will be generated including relevant tests for association between the individual variables mentioned above and continuous values of suPAR and hsCRP, respectively.

We will fit Cox proportional hazards models to assess the association between preoperative suPAR and hsCRP-values and death from any cause. The goodness-of-fit of the Cox model will be investigated and the model will be adapted as required to fulfil the model assumptions. The model will be adjusted for sex, age, current smoker, AMI within 90 days, diabetes mellitus, creatinine, CPB time and aorta clamp time. 30-days survival

will be modelled using logistic regression. If we cannot find Cox and/or logistic models that fit the data, alternative models will be considered.

Receiver operating characteristics (ROC) curve and area under the curve (AUC) analysis will be performed comparing EuroSCORE II, suPAR, hsCRP, suPAR+hsCRP, EuroSCOREII+suPAR, EuroSCOREII+hsCRP and EuroSCOREII+suPAR+hsCRP. Sensitivity and specificity values will be included.

Regression analysis between suPAR and hsCRP measurement will be performed.

Kaplan-Meier survival plots will be generated for the 4 quartiles of suPAR and hsCRP, respectively.

Two supplementary tables will be generated presenting the pre-, peri- and postoperative variables divided into the 4 quartiles of suPAR and hsCRP, respectively.

A two-sided p value <0.05 will be considered significant.

QUALITY ASSURANCE

An internal quality control of the reliability of the biochemical analyses of the study biomarkers will be performed at the department of clinical biochemistry. Since the remaining clinical data is extracted from well-established electronic databases, no internal validation on the data will be performed.

An experienced statistician from the project group will handle the statistical analysis, to ensure quality of the statistical methodology and processing of data.

EXPECTED OUTCOMES OF THE STUDY

The results of this study are expected to provide further knowledge on the applicability of the biomarkers suPAR and hsCRP - specific in the setting of cardiovascular surgery. These inflammatory biomarkers might be able to reveal a pro-inflammatory disease state that represents a risk in patients undergoing cardiovascular surgery. We expect that preoperative high levels of suPAR and hsCRP are associated with death after cardiac surgery.

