### **5 ENDPOINTS AND COVARIATES**

### Primary objective

1. Association of preoperative suPAR values in relation to the censored time-to-event outcome "death from any cause" [Time Frame: from index surgery to date of data collection]

Secondary objectives:

- 2. Association of preoperative hsCRP values in relation to the censored time-to-event outcome "death from any cause" [Time Frame: from index surgery to date of data collection]
- 3. Assess whether adding suPAR, hsCRP or combined suPAR+hsCRP measurements improves predictive accuracy of EuroSCORE II [Time Frame: from index surgery to 30 days postoperative]
- 4. Sensitivity of the models; EuroSCORE II, suPAR, hsCRP, suPAR+hsCRP, EuroSCOREII+suPAR, EuroSCOREII+hsCRP and EuroSCOREII+suPAR+hsCRP in relation to the time-to-event outcome "death from any cause" [Time Frame: from index surgery to 30 days postoperative]
- 5. Specificity of the models; EuroSCORE II, suPAR, hsCRP, suPAR+hsCRP, EuroSCOREII+suPAR, EuroSCOREII+hsCRP and EuroSCOREII+suPAR+hsCRP in relation to the time-to-event outcome "death from any cause" [Time Frame: from index surgery to 30 days postoperative]
- 6. Asses association between suPAR and hsCRP measurements

Other outcome measures:

- 1. 30 days mortality measured by a yes/no question of "all-cause mortality" [Time Frame: from index surgery to 30 days]
- 2. 1-year mortality measured by a yes/no question of "all-cause mortality" [Time Frame: from index surgery to 1 year]

Covariates to be used in the analysis in order of priority according to number of events:

1. Sex (female/male), age (continuous), current smoker (status preoperative: yes/no), diabetes mellitus (status preoperative: yes/no), creatinine (preoperative: continuous), CPB time (continuous) and aorta clamp time (continuous), AMI within 90 days (status preoperative: yes/no)

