### 7.1 STATISTICAL PROCEDURES

A table 1 with patient characteristics for the entire study population will be generated presenting frequencies (percent), mean  $\pm$  standard deviation (SD), and median (25–75% quartile), where appropriate. This table will include the following variables: age (continuous (years)), sex (male), body-mass-index/BMI (continuous (kg/m^2), diabetes mellitus (NIDDM/IDDM), arterial hypertension (yes), EuroSCORE II value (continuous (%)), smoking status (never/previous/active), precious PCI (yes), NYHA (I-IV), CCS class 4 (yes), left ventricle ejection fraction/LVEF (continuous (%)), Previous cardiac surgery (yes), chronic lung disease (yes), acute myocardial infarction (AMI) within 90 days of surgery (yes), pulmonary hypertension (no, moderate, severe), weight on the intervention (isolated CABG, single non CABG, 2 procedures, 3 procedures), surgery on thoracic aorta (yes), baseline creatinine (continuous ( $\mu$ mol/L)), hsCRP (continuous (mg/L)), suPAR (continuous (ng/mL)),

In addition, the following peri- and postoperative variables will be used for analysis: cardiopulmonary bypass/CPB time (continuous (min)), aorta clamp time (continuous (min)), length of stay – ICU (continuous (hours)), length of stay – Hospitalisation (continuous (days)).

A table 2 will be generated including relevant tests for association between the individual variables mentioned above and continuous values of suPAR and hsCRP, respectively.

We will fit Cox proportional hazards models to assess the association between preoperative suPAR and hsCRPvalues and death from any cause. The goodness-of-fit of the Cox model will be investigated and the model will be adapted as required to fulfil the model assumptions. The model will be adjusted for sex, age, current smoker, AMI within 90 days, diabetes mellitus, creatinine, CPB time and aorta clamp time. 30-days survival will be modelled using logistic regression. If we cannot find Cox and/or logistic models that fit the data, alternative models will be considered.

Receiver operating characteristics (ROC) curve and area under the curve (AUC) analysis will be performed comparing EuroSCORE II, suPAR, hsCRP, suPAR+hsCRP, EuroSCOREII+suPAR, EuroSCOREII+hsCRP and EuroSCOREII+suPAR+hsCRP. Sensitivity and specificity values will be included.

Regression analysis between suPAR and hsCRP measurement will be performed.

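### SAP 7.1 compares EuroSCORE II with four combined models that are, by inference, weighted and scored in the same patients, without optimism correction, so their apparent 30-day AUCs are too favourable on average

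*SAP*

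**What the plan says.** SAP section 5, secondary objective 3, is to "Assess whether adding suPAR, hsCRP or combined suPAR+hsCRP measurements improves predictive accuracy of EuroSCORE II" at 30 days. Objectives 4 and 5 ask for the sensitivity and specificity of the same models. (The protocol numbers these three as secondary objectives 2 to 4.)

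The planned answer is in SAP 7.1: "Receiver operating characteristics (ROC) curve and area under the curve (AUC) analysis will be performed comparing EuroSCORE II" with six alternatives. The protocol's section on data management and statistical analysis has the same list: "comparing EuroSCORE II, suPAR, hsCRP, suPAR+hsCRP, EuroSCOREII+suPAR, EuroSCOREII+hsCRP and EuroSCOREII+suPAR+hsCRP". SAP 7.1 adds that "Sensitivity and specificity values will be included", with no cut-off rule. The only model named for this horizon is in the line "30-days survival will be modelled using logistic regression", with a fallback: "If we cannot find Cox and/or logistic models that fit the data, alternative models will be considered".

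The protocol states the result it looks for: "We also expect that suPAR and/or hsCRP can provide increased predictive accuracy of the risk model EuroSCORE II".

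Neither document mentions bootstrap, cross-validation, a split sample, shrinkage, a validation cohort or weights taken from elsewhere.

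**The concern.** Three of the seven entries (EuroSCORE II, suPAR, hsCRP) are single scores. An AUC depends only on ranks, so with the direction set in advance they can be scored without estimating anything here. The other four (suPAR+hsCRP, EuroSCORE II+suPAR, EuroSCORE II+hsCRP, and EuroSCORE II with both) need weights. The SAP does not say where the weights come from. With one cohort, logistic regression and no external weights, they can only be estimated in these patients.

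The comparison then sets models scored on their own training data against a score that was not trained there. The fitted models gain from chance patterns, and the error runs in the direction the protocol expects. A reader would use the reported AUC gain to judge whether measuring the markers is worthwhile, so the size of that estimate matters even though the objective is secondary.

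**Working it through.** **There is no planned figure to reproduce.** The documents give no 30-day mortality, EuroSCORE II AUC, expected gain or power. The size must be simulated under stated assumptions.

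**Inputs**
- N = 951, from the protocol title ("Predictive value of suPAR and hsCRP on postoperative mortality in 951 patients undergoing elective on-pump cardiac surgery"); the text elsewhere says about 1000.
- Assumed 30-day mortality 1%, 2%, 3% and 4%: 951 × 0.01 = 9.5, 951 × 0.02 = 19.0, 951 × 0.03 = 28.5 and 951 × 0.04 = 38.0, that is 10, 19, 29 and 38 deaths.
- Assumed EuroSCORE II AUC 0.75 (also 0.70 and 0.80), with a binormal score and independent normal markers.

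**Definitions**
- Apparent gain = AUC of the fitted model − AUC of EuroSCORE II, both in the fitting cohort.
- True change = the same difference for the same weights in new patients.
- Optimism = apparent gain − true change.

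**Step 1. Two worthless markers added to EuroSCORE II, AUC 0.75**

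| Deaths | 10 | 19 | 29 | 38 |
|---|---|---|---|---|
| Mean apparent gain | +0.026 | +0.014 | +0.009 | +0.007 |

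The gain was above zero in 83–86% of datasets, while the fitted models' true change was negative. Over all 12 combinations of death count and AUC the mean was +0.005 to +0.034. One worthless marker gave +0.002 to +0.019. The markers-only model, with both markers worthless, showed AUCs of 0.61, 0.58, 0.57 and 0.56 instead of 0.50.

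**Step 2. Correlated predictors.** Assumed correlations were 0.35, 0.20 and 0.30, with EuroSCORE II AUC about 0.76. At 2% mortality, with no marker effect beyond EuroSCORE II, the full model's apparent gain was +0.0128 and its true change −0.0126: optimism 0.0128 + 0.0126 = 0.0254. At 5% it was 0.0053 + 0.0053 = 0.0106. Mean optimism was positive for all four combinations at every mortality tried (1–5%), with and without real marker effects.

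**Step 3. What a bootstrap correction does** (AUC 0.75, two markers, 400 datasets with 100 resamples each, resamples with fewer than 4 deaths skipped). For the real-marker case, shifts of 0.4 and 0.2 SD are assumed. AUC 0.75 corresponds to a separation of √2 × 0.6745 = 0.954 SD. Adding the markers gives √(0.954² + 0.4² + 0.2²) = 1.054, so AUC = Φ(1.054/√2) = 0.772 and the population gain is +0.022.

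| Deaths | 10 | 19 | 38 |
|---|---|---|---|
| Worthless: apparent gain | +0.027 | +0.014 | +0.007 |
| Worthless: corrected gain | −0.017 | −0.012 | −0.007 |
| Worthless: true change of fitted model | −0.027 | −0.013 | −0.007 |
| Real: apparent gain | +0.046 | +0.033 | +0.029 |
| Real: corrected gain | +0.004 | +0.010 | +0.018 |

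For worthless markers, the corrected value misses the fitted model's true change by +0.010, +0.001 and 0.000. The apparent value misses it by +0.054, +0.027 and +0.014. Against the population gain of +0.022, the apparent value is off by +0.024, +0.011 and +0.007, and the corrected value by −0.018, −0.012 and −0.004.

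**Step 4. Tests, with worthless markers.** A likelihood-ratio test of the added terms rejected in 4.9–5.7% of datasets (4.5–6.7% over the 12 scenarios). A DeLong comparison, assumed because the plan names no AUC test, rejected in 3.1%, 1.4%, 1.3% and 1.1%. With real markers, power was 22–65% for the likelihood-ratio test and 7–17% for DeLong.

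**Step 5. Sensitivity and specificity.** At a same-data cut-off giving 80% specificity, sensitivity of the two-marker model was too high by +0.078, +0.047, +0.028 and +0.024 at 10, 19, 29 and 38 deaths. EuroSCORE II was essentially unbiased (−0.009 to +0.005), and specificity bias was at most 0.002. In the bootstrap check (10, 19, 38 deaths), the sensitivity bias fell from +0.092, +0.052 and +0.028 to +0.017, +0.010 and +0.005.

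A cut-off fixed on sensitivity behaves differently. For any continuous score with the cut-off at the k-th highest of m deaths, apparent sensitivity is k/m and expected sensitivity in new deaths is k/(m+1). With m = 10 and k = 8 this is 0.800 against 0.727, a bias of +0.07. With m = 38 and k = 31 it is 0.816 against 0.795, a bias of +0.02. This applies to EuroSCORE II and the single markers as well.

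**The case against.** The strongest reply is that little follows from the bias.

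- **No excess false claims.** The plan judges significance at two-sided p < 0.05, and neither plausible test rejects too often (step 4). This stands. A reader might infer from a gain appearing in 83–86% of null datasets that the study will usually claim an improvement falsely. The documents do not support that: a positive apparent difference is not their criterion for significance.
- **The correction overshoots.** Measured against what the markers add in the population, the corrected value is about as far below as the apparent value is above. At 19 deaths with real markers the errors are −0.012 and +0.011. This also stands. The correction estimates a different quantity, the performance of the model as fitted. Both values should therefore be shown, and a test should decide whether the markers add value.
- **The shift is small.** The sampling standard error of the EuroSCORE II AUC was about 0.04 to 0.07 in the same kind of simulation. It belongs to one AUC, not to the paired difference, so it shows scale only. At 29 to 38 deaths with AUC 0.75 the two-marker apparent gain is below 0.01.
- **Same-patient fitting is inferred.** True, but the documents offer no other source of weights.
- **suPAR+hsCRP does not contain EuroSCORE II.** Its difference from EuroSCORE II can be negative, so only its AUC, not a gain, is called too favourable here.

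**Conclusion.** The point holds as one about point estimates. The apparent AUCs of the four combined models, and the apparent gains of the three that contain EuroSCORE II, are too favourable on average as descriptions of the fitted models. With two worthless markers, 951 patients and AUC 0.75, the mean gain is about +0.026 at 10 deaths and +0.007 at 38. The direction held in every scenario tried. The size depends on a death count and an AUC that the documents do not give, and is small at the higher death counts.

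The consequence is confined to secondary objectives 3 and 4 (SAP numbering). Specificity is essentially unaffected, and so is the primary suPAR Cox analysis, which does not use these models.

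Two further inferences are not supported. SAP section 8 declines internal validation, but of data extracted from databases; it is not a decision against validating models. And the plan states no cut-off rule, so it cannot be said that cut-offs will be tuned to these data. This is a cheap improvement to secondary analyses.

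**What to change.** Add to SAP 7.1:

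1. For the four combined models, report the bootstrap optimism-corrected AUC beside the apparent AUC. For the three EuroSCORE II combinations, also report the corrected AUC difference from EuroSCORE II. Refit the logistic model in each resample; include the alternative-model fallback only if it is first written as a fixed algorithm. State that the corrected value describes the fitted model and tends to fall below the markers' population gain when deaths are few.
2. Name a likelihood-ratio test of the added biomarker terms as the test of whether the markers add value.
3. If sensitivity is reported for the fitted models, take it at a prespecified fixed specificity and apply the same correction. A same-data cut-off chosen by maximising performance or by fixing sensitivity would inflate sensitivity for EuroSCORE II and the single markers too.

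The cost is a few sentences and one bootstrap loop, with no new data. The figures will look slightly less favourable. Intervals for the corrected difference are not requested, since they need further resampling and their coverage was not examined.

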### 2 DATA SOURCE

PATS: BMI, procedure codes, CPB time and aorta clamp time, procedure date, date and time for admission and discharge ICU.

ICCA: length of stay ICU (if missing in PATS)

Biochemical data: creatinine

The Danish National Patient Register: age, sex, date of death

Perfusionist charts: CPB time and aorta clamp time (if missing in PATS)

Sundhedsplatformen: type of surgery, previous PCI, AMI within 90 days of surgery, hypertension, diabetes mellitus, smoking status, left ventricle ejection fraction (LVEF), NYHA, CCS, date of discharge hospitalisation, length of stay ICU (if missing in PATS), and the following defined according to the EuroSCORE II; extracardiac arthropathy, mobility status, previous cardiac surgery, chronic lung disease, active endocarditis, critical preoperative state and pulmonary hypertension,

The blood samples for the study were drawn preoperatively or within the first 24 hours of surgery (only preoperative data for hsCRP included) and stored in the Persimune Biobank or two other biobanks at Dept. Cardiothoracic Anaesthesiology and Dept. Cardiothoracic Surgery, Rigshospitalet (registered [name], PhD and [name], respectively). The analysis is performed using commercially available analyses (suPARnostic® kit (validated to measure suPAR concentrations between 0.6 and 22 ng/mL) (ViroGates)). HsCRP will be measured by high sensitivity CRP assays (Tina-quant hsCRP latex assay (validated to measure CRP concentrations between 0.3 - 20 mg/L) (Roche/Hitachi)). In patients with CRP>20 mg/L a regular CRP-measurement will be performed.

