## 4 ANALYSIS SETS/ POPULATIONS/SUBGROUPS

The population includes adult patients ( $\geq$ 18 years) undergoing cardiac surgery at department of Cardiothoracic Surgery at Rigshospitalet, Copenhagen University hospital, Denmark.

Inclusion Criteria:

• Patients planned for elective on-pump cardiac surgery (isolated coronary artery bypass graft (CABG), single and multiple valvular procedures, combined CABG and valvular surgery, and others) and have given informed consent on delivering a blood sample for the biobank.

Exclusion Criteria:

• Peroperatively cancelling the surgery due to anatomic challenging findings, sudden change to offpump coronary artery bypass (OPCAB) surgery, death prior to surgery and project blood samples not available.

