### 6 HANDLING OF MISSING VALUES AND OTHER DATA CONVENTIONS

Missing data is expected to be at random and due to device fault or misplaced registration. No data are extracted from questionnaires or physical follow-up by the patients. Missing values will be handled using pairwise deletion, still analysing all cases with the variable of interest.

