Kaplan-Meier survival plots will be generated for the 4 quartiles of suPAR and hsCRP, respectively.

Two supplementary tables will be generated presenting the pre-, peri- and postoperative variables divided into the 4 quartiles of suPAR and hsCRP, respectively.

A two-sided *p* value <0.05 will be considered significant.

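### Added value over EuroSCORE II at 30 days: the plan ties no test of a biomarker given EuroSCORE II to this objective and plans no optimism correction, leaving only an apparent AUC comparison

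*SAP*

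**What the plan says.** The objective is SAP section 5, secondary objective 3 (number 2 in the protocol's list): "Assess whether adding suPAR, hsCRP or combined suPAR+hsCRP measurements improves predictive accuracy of EuroSCORE II", over the first 30 days after surgery.

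The analysis is in SAP 7.1, repeated in the protocol under Sample size and statistical analyses: "Receiver operating characteristics (ROC) curve and area under the curve (AUC) analysis will be performed comparing EuroSCORE II, suPAR, hsCRP", followed by the four combinations of these three. That makes seven models, three of which add a biomarker to EuroSCORE II.

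Two other statements bear on it:

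- The sentence before the ROC paragraph's companion text names the 30-day model: "30-days survival will be modelled using logistic regression". It gives no covariates. The eight covariates in SAP section 5 do not include EuroSCORE II.
- The only decision rule is general: "A two-sided p value <0.05 will be considered significant" (protocol; the same in the SAP). It is attached to no statistic for this objective.

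Neither document names a test of an AUC difference, a test of a biomarker in a model containing EuroSCORE II, a bootstrap, cross-validation or a validation sample.

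**The concern.** The objective asks whether prediction improves, but the plan does not say which result answers that. Three readings are open.

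- **A.** The AUCs of nested models are compared with a paired DeLong test at 5%. That test treats the fitted scores as fixed and is very conservative when one model is nested in the other.
- **B.** The AUCs are compared descriptively in the data used for fitting. The larger model is then favoured on average. A logistic fit on EuroSCORE II alone (with a positive slope) leaves the ranking of patients unchanged, so essentially all the optimism falls on the model with the extra terms.
- **C.** The biomarker's p-value is taken from the logistic model that also contains EuroSCORE II. This is adequate, but the plan does not present it as the answer.

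Under A, a moderately predictive marker would nearly always be missed. Under B, a useless marker can look like a gain. If the choice is made after the data are seen, the conclusion can depend on it.

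**Working it through.** The plan gives no power, effect size, 30-day mortality or AUC difference for this objective, so there is no figure of its own to reproduce. The size of the problem was found by simulation.

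**Inputs**

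- From the documents: N = 951 (protocol title; the text says about 1000) and two-sided 5%.
- Assumed, because the documents give no values: 30-day mortality 1/2/3%; EuroSCORE II AUC about 0.75 (some ranges also cover 0.80); correlation of marker with EuroSCORE II 0 or 0.3; odds ratio (OR) per SD of the marker, given EuroSCORE II, of 1.0, 1.5 or 2.0.

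**Deaths.** N × mortality: 951 × 0.01 = 9.5; 951 × 0.02 = 19.0; 951 × 0.03 = 28.5.

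**Statistics**

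- Likelihood-ratio test (LRT): 2 × (log-likelihood with marker − log-likelihood without), chi-square with 1 df (2 df for both markers).
- DeLong: z = (AUC with marker − AUC without) / SE of the paired difference.
- Bootstrap-corrected change: apparent AUC change − mean over resamples of (change in the resample − change when the resample's models are applied to the original data).

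**Readings A and C: proportion of datasets significant at 5%, by assumed mortality**

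| Scenario | Test | 1% | 2% | 3% |
|---|---|---|---|---|
| One marker, OR 1.5 | DeLong | 4% | 5% | 6–8% |
| | LRT | 22% | 35–41% | 51–54% |
| One marker, OR 2.0 | DeLong | 13% | 20–23% | 30–35% |
| | LRT | 51–54% | 79–82% | 91–93% |
| Both markers, OR 1.5 each | DeLong | 12% | 17–19% | 25–28% |
| | LRT (2 df) | 35–37% | 57–63% | 75–80% |
| No effect (AUC 0.75 or 0.80) | DeLong | 0.8–1.4% | 0.4–0.8% | 0.3–0.4% |
| | LRT | 4.4–5.7% | 4.4–5.7% | 4.4–5.7% |

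With no effect, DeLong rejects far less often than 5%, which is the sign of conservatism; the LRT is close to 5%. In one set-up (correlation 0.3, OR 1.5) the Wald test of the coefficient, reading C, has power 22/34/51% against 22/35/51% for the LRT. The gap between DeLong and the LRT narrows for strong markers and more deaths: at OR 2.5 it is 58–63% against 99% at 3% mortality, and 83–87% against 100% at 5%.

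**Reading B: one marker with no effect (AUC 0.75)**

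- Mean apparent AUC gain: about 0.015/0.007/0.005. For comparison, a marker with OR 1.5 has a true gain of 0.012–0.018.
- Apparent gain of 0.01 or more (correlation 0): 39/24/16% of datasets.
- The larger model has the lower apparent AUC in 24–28% of datasets, so the bias is an average and not a certainty.

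**Does bootstrap correction help?** (AUC 0.75, correlation 0.3; 250 datasets, 60 resamples each)

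| Marker | Mean AUC change | 1% | 2% | 3% |
|---|---|---|---|---|
| No effect | Apparent | 0.015 | 0.008 | 0.005 |
| | Corrected | −0.009 | −0.007 | −0.004 |
| | In new patients | −0.014 | −0.007 | −0.005 |
| OR 1.5 | Apparent | 0.028 | 0.023 | 0.020 |
| | Corrected | 0.007 | 0.011 | 0.012 |
| | In new patients | 0.004 | 0.010 | 0.012 |

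The 0.008 here against 0.007 above is consistent with the smaller number of datasets. Correction removes most of the optimism at 2% and 3% mortality and part of it at 1%.

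**Multiplicity.** Three added-value tests at 5%, if independent: 1 − 0.95³ = 14.3%. They overlap, so this figure is only a guide.

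**The case against.** The strongest reply is reading C. SAP 7.1 names logistic regression for 30-day survival and then lists the combined models. Fitting EuroSCORE II plus suPAR routinely gives a p-value for suPAR given EuroSCORE II, and the 5% rule exists. For a single marker that p-value performs almost as well as the LRT. This stands: the plan does not rule out a sound analysis. What remains is that it does not name that p-value as the answer, while the analysis it does state is an AUC comparison with no correction.

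The second reply is that the better test is also weak. At OR 1.5 the LRT misses the marker more often than not at 1% and 2% mortality, and about half the time at 3%. This also stands. In addition, a percentile bootstrap interval for the AUC change averaged 0.16/0.10/0.07 wide in a check at OR 1.5, so it would settle little.

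Third, a significant LRT shows added information and need not mean better prediction. This is correct, and the fix therefore needs a rule that joins the test and the AUC change.

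A reader might draw three stronger conclusions that the documents do not support:

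- **That a DeLong test is planned.** Neither document mentions one.
- **That the compared models will use different patients.** SAP 6 says "Missing values will be handled using pairwise deletion, still analysing all cases with the variable of interest", and SAP 2 describes samples "drawn preoperatively or within the first 24 hours of surgery (only preoperative data for hsCRP included"). The exclusion in SAP 4 ("death prior to surgery and project blood samples not available") does not remove patients whose sample was not preoperative. But pairwise deletion can equally mean complete cases per comparison, a paired test needs one patient set anyway, and the share without preoperative hsCRP is not given.
- **That the QC statement declining internal validation refers to the models.** It concerns the extracted clinical data.

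**Conclusion.** The concern holds as a gap in the stated analysis of one secondary objective. That no test given EuroSCORE II is tied to the objective, and that no optimism correction is planned, rests on the text alone.

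The size rests on the assumed mortality, AUC, correlation and odds ratios. On those assumptions, with OR 1.5, choosing reading A over reading C cuts power at least fivefold (22% against 4% at 1% mortality). Under reading B, the mean apparent gain from a useless marker at 1% mortality (about 0.015) is as large as the true gain from a marker with OR 1.5 (0.012–0.018); it is smaller at 2% and 3%.

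It would go too far to say that the plan commits to a wrong test or that its answer will be wrong: the harm is a risk from what is left open. Nor does the fix make the objective well powered. The primary Cox analysis is not affected.

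**What to change.** In SAP 7.1:

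1. **Test.** Use likelihood-ratio tests of the logistic model for death within 30 days with EuroSCORE II alone against that model plus suPAR (1 df), plus hsCRP (1 df) and plus both (2 df). Fix the coding of EuroSCORE II and of the markers in advance.
2. **Patients.** Fit each compared pair on one common set of patients who have all the values that pair needs, and say so in SAP 6.
3. **Size of the gain.** Report the AUC change with bootstrap optimism correction (both models refitted in each resample) and an interval whose construction is stated. Do not base the conclusion on a DeLong p-value for nested models.
4. **Rule.** Claim improved predictive accuracy only if the likelihood-ratio test is significant and the corrected AUC change is positive. If the test is significant but the corrected change is not positive, report added information only. If the test is not significant, make no claim, and do not read it as evidence of no value.
5. **Multiplicity.** Treat the three comparisons as secondary and state whether they are adjusted.

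The cost is SAP wording and a bootstrap. No new data are needed, and the ROC analysis already requires these models. There are downsides. The hsCRP comparisons may use fewer patients, intervals will be wide with few deaths, and only part of the optimism is removed. The joint rule cannot have more power than the likelihood-ratio test alone.
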